11.5 End of Study (EOS)

At the conclusion of the UDS test, the subject is no longer required to undergo any further study-related procedures.

Once a site has completed its target recruitment, the sponsor (Laborie) will schedule a time to close-out the site, either in person or by telephone as per the monitoring plan. All study related files will be collected and reviewed for completeness. The EOS is considered the point when all subjects have been followed-up and data collection completed.

12 STATISTICAL CONSIDERATIONS

12.1 Primary Safety and effectiveness Endpoints

12.1.1 Primary Effectiveness Endpoint

The primary effectiveness endpoint is a binary clinician response after each UDS study using the T-DOC® NXT Catheter to determine whether the ability to measure UDS pressure was clinically adequate (success) or inadequate (failure). The primary effectiveness hypothesis is a comparison of the lower bound for the estimate of the success rate to a minimally acceptable target value of 75%:

H_0 : Effectiveness Success Rate is $\leq 75\%$

versus

H_A : Effectiveness Success Rate is $> 75\%$

This hypothesis will be evaluated by comparing the lower limit of the 1-sided 95% Clopper-Pearson confidence interval to 75%. The null hypothesis will be rejected if the lower limit of the 1-sided 95% Clopper-Pearson confidence interval is $> 75\%$, which indicates that a rate $\leq 75\%$ would be inconsistent with the trial findings.

12.1.2 Primary Safety Endpoint

The primary safety endpoint is a binary clinician response after each UDS study using the T-DOC® NXT Catheter to determine whether the safety of the device was clinically adequate (success) or inadequate (failure). The primary safety hypothesis is a comparison of the lower bound for the estimate of the success rate to a minimally acceptable target value of 75%:

H_0 : Safety Success Rate is $\leq 75\%$

versus

H_A : Safety Success Rate is $> 75\%$

This hypothesis will be evaluated by comparing the lower limit of the 1-sided 97.5% Clopper-Pearson confidence interval to 75%. The null hypothesis will be rejected if the lower limit of the 1-sided 97.5% Clopper-Pearson confidence interval is $> 75\%$, which indicates that a rate $\leq 75\%$ would be inconsistent with the trial findings.

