2.2.1 Primary Safety and Effectiveness Endpoints

Primary Effectiveness Endpoint

The primary effectiveness endpoint is a binary clinician response after each UDS study using the T-DOC® NXT Catheter to determine whether the ability to measure UDS pressure was clinically adequate (success) or inadequate (failure). The primary effectiveness hypothesis is a comparison of the lower bound for the estimate of the success rate to a minimally acceptable target value of 75%.

H_0 : Effectiveness Success Rate is $\leq 75\%$

versus

H_A : Effectiveness Success Rate is $> 75\%$

This hypothesis will be evaluated by comparing the lower limit of the 1-sided 95% Clopper-Pearson confidence interval to 75%. The null hypothesis will be rejected if the lower limit of the 1-sided 95% Clopper-Pearson confidence interval is $> 75\%$, which indicates that a rate $\leq 75\%$ would be inconsistent with the trial findings.

Primary Safety Endpoint

The primary safety endpoint is a binary clinician response after each UDS study using the T-DOC® NXT Catheter to determine whether the safety of the device was clinically adequate (success) or inadequate (failure). The primary safety hypothesis is a comparison of the lower bound for the estimate of the success rate to a minimally acceptable target value of 75%:

H_0 : Safety Success Rate is $\leq 75\%$

versus

H_A : Safety Success Rate is $> 75\%$

This hypothesis will be evaluated by comparing the lower limit of the 1-sided 95% Clopper-Pearson confidence interval to 75%. The null hypothesis will be rejected if the lower limit of the 1-sided 95% Clopper-Pearson confidence interval is $> 75\%$, which indicates that a rate $\leq 75\%$ would be inconsistent with the trial findings.

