12.3 Sample Size Determination & Power

The null hypotheses for the primary safety and the primary effectiveness endpoints are designed to rule out success rates $\leq 75\%$. There will be no type I error adjustment for simultaneous testing of these endpoints within the same trial. Based on clinical judgement and previous testing, the true success rate for both safety and efficacy is assumed to exceed 95%. Thus, the power calculation is identical for the safety and effectiveness endpoints, and a true success rate of 96% is assumed for each endpoint.

Analysis of 20 subjects would provide 81% power to rule out a success rate $\leq 75\%$ when the true success rate is assumed to be 96%, based on a 1-sided test with type I error rate of 5%. This study requires a minimum of 20 subjects to ensure adequate power, but the final sample size will be based on site enrolment capabilities. If 30 subjects or 40 subjects are enrolled, the power to rule out a success rate $\leq 75\%$ will be 96% and 99%, respectively (Fleiss, J.L. *et al.*, 2003).

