To evaluate the usability of the device by collecting clinical user feedback and evaluating the following subjective measures using defined ordinal scales: ease of use, ease of insertion, presence of artefacts, stability of the tracing, perceived time savings, ease of voiding around catheter, presence of use errors and overall satisfaction.	The usability performance endpoint will be captured in a questionnaire format. The trained clinical users will rate the T-DOC® NXT performance on a scale of 1-5 on the study outcome questionnaire.
Exploratory Objective 2	
To explore whether the newly designed, smaller sized T-DOC® NXT catheters causes undue discomfort based on subjective subject feedback regarding the discomfort and pain level, for those able to communicate such feedback.	This exploratory endpoint will be measured by collecting patient feedback regarding the level of discomfort and pain experienced during their Urodynamic test using the Numeric Pain Rating Scale (NPRS). Patients capable of providing feedback on a scale, will grade their discomfort/pain at 5 or lower, on the NPRS from 0 ("No Hurt") to 10 ("Hurts worst").

Analysis Populations

All subjects enrolled and completed the urodynamic procedure will be considered in the final analysis. Enrolled subjects who do not undergo the urodynamic procedure or begin the urodynamic procedure but do not complete it (for any reason determined by the investigator to be unrelated to the T-DOC® NXT catheters) will not be included in the final analysis and can be replaced.

If any CRFs are found to be incomplete, the study monitor will follow-up as to the reasoning. If for some reason a clinical user is unable to complete their questionnaire, the questions they have completed will be included in the analysis.

Primary Endpoint

The primary safety and effectiveness endpoint is a binary clinician response after each UDS study using the T-DOC® NXT catheter to determine whether the ability to measure UDS pressure was clinically adequate (success) or inadequate (failure).

In the statistical analysis plan, the null hypotheses for the safety and effectiveness endpoints are designed to rule out success rates $\leq 75\%$.

The allowable Type I error (α) for each hypothesis will be 5% (1-sided), and the Type II error is calculated to be 10% (90% power).

Safety and effectiveness will be evaluated separately via the following sets of hypotheses:

Primary Hypothesis for Safety

H_0 : Safety Success Rate is $\leq 75\%$

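### Primary safety is judged against a 1-sided 95% limit in Protocol 2.2.1 and a 1-sided 97.5% limit in Protocol 12.1.2, so the same data can pass or fail

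*Protocol*

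**What the plan says.** Protocol 2.2.1 and Protocol 12.1.2 define the same safety endpoint, a binary clinician rating after each urodynamic study. They use the same hypotheses and the same 75% benchmark, but different confidence levels.

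- **Protocol 2.2.1:** "This hypothesis will be evaluated by comparing the lower limit of the 1-sided 95% Clopper-Pearson confidence interval to 75" (per cent).
- **Protocol 12.1.2:** "This hypothesis will be evaluated by comparing the lower limit of the 1-sided 97.5% Clopper-Pearson confidence interval to 75" (per cent). The next sentence repeats the level in the rejection rule: "The null hypothesis will be rejected if the lower limit of the 1-sided 97.5% Clopper-Pearson confidence interval is" above 75%.
- **Effectiveness (Protocol 2.2.1 and 12.1.1):** 1-sided 95% in both places.
- **Protocol 12.3:** "There will be no type I error adjustment for simultaneous testing of these endpoints within the same trial"; "Thus, the power calculation is identical for the safety and effectiveness endpoints"; and the power is "based on a 1-sided test with type I error rate of 5" per cent.
- **SAP, Primary Endpoint:** "The allowable Type I error (α) for each hypothesis will be 5% (1-sided". It names neither the interval method nor a confidence level for the primary tests. It declares success only if both null hypotheses are rejected.
- **Protocol 12.5:** leaves the details of testing to the SAP, but also says the data will be analysed as set out in Section 12.1.

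**The concern.** This is the decision threshold of a primary endpoint, and two current sections of one protocol set it differently. An analyst who works from Protocol 12.1, as 12.5 directs, would use 97.5% for safety. One who works from Protocol 2.2.1 or the SAP's error rate would use 95%.

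The 97.5% does not read as a multiplicity adjustment. Effectiveness stays at 95%, and 12.3 rules out any adjustment.

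Three features of the design make an unsettled threshold riskier. The study is unblinded (Protocol 12.4), the sponsor's own team determines whether the endpoints were met (9.2), and the final sample size is open between 20 and 40 with an informal look at 20 (12.3, 12.7). With two thresholds in the text, the choice between them could be made after the results are known.

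**Working it through.** **Inputs**

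- Benchmark 75% (Protocol 2.2.1, 12.1.2).
- Assumed true success rate 96% for each endpoint (12.3).
- Sample size 20 to 40 (2.1, 7.4).
- One-sided α of 0.05 (2.2.1, 12.3, SAP) or 0.025 (12.1.2).
- Stated power 81%, 96% and 99% at 20, 30 and 40 subjects (12.3).

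**Formulas**

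- Clopper-Pearson lower limit for x successes in n: L = BetaInv(α; x, n − x + 1).
- Pass mark c: the smallest x with L > 0.75.
- Power: P(X ≥ c) for X ~ Binomial(n, 0.96).
- Attained type I error: P(X ≥ c) for X ~ Binomial(n, 0.75).

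**Step 1: reproduce the plan's power at α = 0.05**

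- n = 20: c = 19. Power = 0.96^20 + 20 × 0.96^19 × 0.04 = 0.4420 + 0.3683 = 0.8103. Stated: 81%.
- n = 30: c = 27, power 96.9%. Stated: 96%.
- n = 40: c = 35, power 99.5%. Stated: 99%.

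All three agree to within one percentage point. A normal approximation at α = 0.05 does not fit at n = 20: it gives 87.7% without and 72.2% with continuity correction. The plan's figures therefore rest on the exact test at 1-sided 5%.

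**Step 2: repeat at α = 0.025**

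| n | Pass mark, 95% limit | Pass mark, 97.5% limit | Power, 95% | Power, 97.5% | Stated power |
|---|---|---|---|---|---|
| 20 | 19 | 19 | 81.0% | 81.0% | 81% |
| 23 | 21 | 22 | 93.8% | 76.6% | none |
| 26 | 24 | 25 | 91.6% | 72.1% | none |
| 30 | 27 | 28 | 96.9% | 88.3% | 96% |
| 40 | 35 | 36 | 99.5% | 97.9% | 99% |

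**Step 3: data on which the rules disagree**

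- 27/30: L = 76.1% at the 95% level (pass), 73.5% at the 97.5% level (fail).
- 35/40: L = 75.5% (pass), 73.2% (fail).
- 19/20: L = 78.4% and 75.1%, so it passes under both.

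**Step 4: all sample sizes from 20 to 40**

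The rules differ wherever the attained type I error of the 95% rule exceeds 0.025. At n = 30, for example, P(X ≥ 27) = 0.0374 and P(X ≥ 28) = 0.0106 under a 75% rate. At n = 20, P(X ≥ 19) = 0.0243 already satisfies both levels.

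- Different at 13 sizes: 23–26, 29–32, 34–37 and 40, each time by exactly one success.
- Identical at 8 sizes: 20–22, 27, 28, 33, 38 and 39.

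**Step 5: chance of landing on the disputed count**

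Because the pass marks differ by one, this chance is the difference between the two powers. At a true rate of 96%:

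- n = 26: 0.9160 − 0.7208 = 0.195, the largest in the range.
- n = 30: 0.9694 − 0.8831 = 0.086.
- n = 40: 0.9951 − 0.9790 = 0.016.
- n = 20: 0.

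**The case against.** The best defence is that the rest of the plan already shows which level is meant. Protocol 2.2.1, Protocol 12.3 and the SAP all work at 1-sided 5%, and the exact test reproduces the stated power at 30 subjects only at that level. Protocol 12.5 leaves testing details to the SAP, so an analyst following the SAP would use 5%. The two mentions of 97.5% are adjacent sentences in one paragraph, most plausibly a leftover.

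The practical reach is also limited. Nothing changes at the required minimum of 20 subjects. Elsewhere only one count per sample size is affected. At 40 subjects the power gap is about one percentage point. The stray level is conservative: the attained type I error stays below 5% under either rule (at n = 30, 3.7% against 1.1%).

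All of this is correct, and it makes 95% the likely intention. It does not remove the conflict. The SAP says in its Introduction that testing procedures and success criteria need more detail, but it then supplies an error rate without naming the interval and without overriding 12.1.2. Protocol 12.5 still points to the section that holds the 97.5%. That the stricter reading is conservative does not help if the threshold can be chosen after the data are seen.

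**Conclusion.** The contradiction is real, lies in current text and affects a primary pass/fail rule. It should be corrected before analysis. It changes the required number of safety successes at 13 of 21 permitted sample sizes, by one success each. At the assumed 96% success rate, the chance of a result on which the two rules disagree runs from zero (including at 20 subjects) to 19.5% (at 26).

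If 12.1.2 governs, the stated safety power is materially wrong at 30 subjects (88.3%, not 96%) and slightly wrong at 40 (97.9%, not 99%). At 23 to 26 subjects it would be 72% to 77%, below the 81% given for the minimum sample size.

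These figures assume the exact Clopper-Pearson rule, independent subjects and the protocol's 96% true rate. The pass marks and the example limits do not depend on the 96%.

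**What to change.** The sponsor should confirm the intended level without reference to results, and then make the documents agree.

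- **If 95% was intended, as most of the text indicates:** change both 97.5% entries in Protocol 12.1.2 to 95%. Add one sentence to the SAP's Primary Endpoint section: each endpoint passes if the lower limit of its 1-sided 95% Clopper-Pearson interval exceeds 75%. The power figures can stand.
- **If 97.5% was intended for safety:** change the safety paragraph of Protocol 2.2.1 and the SAP's 5% for the safety hypothesis. Revise the statements in 12.3 that the error rate is 5% and that the power calculation is the same for both endpoints. Restate safety power as about 81%, 88% and 98% at 20, 30 and 40 subjects.

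The SAP allows revisions until database lock, so the SAP change belongs before then. If lock has passed, the choice and its reason should be reported under Protocol 12.6. The cost is a short text correction, one SAP sentence and the IRB notification that Protocol Section 16 requires for a protocol change. No patients or data are added.

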12.2 Exploratory Analyses

- Assess subjective patient feedback regarding the discomfort and pain levels
- Assess user impressions of device performances based on their individual experience with existing ACC catheters by evaluating the following subjective measures: ease of use, ease of insertion, presence of artefacts, presence of cough/valsalva response, measurements and tracings of urethral pressure profiles, stability of the tracing, perceived time savings, ease of voiding around catheter, presence of use errors and overall satisfaction

12.3 Sample Size Determination & Power

The null hypotheses for the primary safety and the primary effectiveness endpoints are designed to rule out success rates $\leq 75\%$. There will be no type I error adjustment for simultaneous testing of these endpoints within the same trial. Based on clinical judgement and previous testing, the true success rate for both safety and efficacy is assumed to exceed 95%. Thus, the power calculation is identical for the safety and effectiveness endpoints, and a true success rate of 96% is assumed for each endpoint.

Analysis of 20 subjects would provide 81% power to rule out a success rate $\leq 75\%$ when the true success rate is assumed to be 96%, based on a 1-sided test with type I error rate of 5%. This study requires a minimum of 20 subjects to ensure adequate power, but the final sample size will be based on site enrolment capabilities. If 30 subjects or 40 subjects are enrolled, the power to rule out a success rate $\leq 75\%$ will be 96% and 99%, respectively (Fleiss, J.L. *et al.*, 2003).

12.4 Randomization / Blinding

Randomization and/or blinding is not utilized in this study based on study design.

12.5 Analysis Plan

A Statistical Analysis Plan containing the details of the analyses and hypothesis testing will be finalized prior to database lock. All subjects who complete the UDS study will be considered in the final analysis. Data will be analysed as discussed in Section 12.1 above.

If any CRFs are found to be incomplete, the study monitor will follow-up as to the reasoning. If for some reason a clinical user is unable to complete their questionnaire, the questions they have completed will be included in the analysis. Data will be monitored as the study progresses, please refer to Section 7.7 for details about suspension or premature termination.

12.6 Deviations

In any event there are deviations from the original statistical plan, they will be described and justified in the final report.

12.7 Early Stopping

An informal interim data analysis will be conducted once 20 subjects have been recruited in order validate the product design meets the user requirements.

There are currently no criteria for stopping the study early on statistical grounds, however please refer to Section 7.7 for details about suspension or premature termination.

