Study end point	Once the minimum subject recruitment goal is met, the sponsor will be informed. The site will have an option to continue recruitment until the maximum is reached, or the 8 week recruitment period closes, whichever occurs first. There will be a site monitoring visit(s) as per the monitoring plan

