9.2 Methods of Assessment

A T-DOC® NXT air-charged catheter will be used to assess and record bladder and abdominal pressures which are in turn used by the clinician to identify UDS events. These measurements will be recorded using a LABORIE UDS system. The resulting interpretations regarding safety, effectiveness, and usability will be made by the physician overseeing the subject's case.

All study outcome data captured will be compiled and analysed by the LABORIE study team to determine if the endpoints were successfully achieved based on whether the null hypotheses were accepted or rejected.

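### The safety endpoint has two decision limits: a 1-sided 97.5% limit in protocol 12.1.2, but 95% in 2.2.1 and a 1-sided 5% test in 12.3 and the SAP

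*Protocol*

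**What the plan says.** **Safety limit.** Protocol 2.2.1 compares the lower 1-sided 95% Clopper-Pearson limit with 75% for effectiveness and for safety. Section 12.1.1 repeats 95% for effectiveness. Section 12.1.2 gives 97.5% for safety, in both sentences that state the decision rule. Section 12.5 directs the analysis to section 12.1. Section 12.3 treats the two endpoints alike, with no adjustment for testing both, and gives power "based on a 1-sided test with type I error rate of 5"%: 81% at 20 subjects, 96% at 30 and 99% at 40, for a true rate of 96%. The SAP (Primary Endpoint) sets a 1-sided 5% error for each hypothesis, requires both nulls to be rejected, and names no interval.

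**Interim and final N.** Section 12.7 states: "An informal interim data analysis will be conducted once 20 subjects have been recruited". It gives a design-validation purpose and adds: "There are currently no criteria for stopping the study early on statistical grounds". In 2.1, once the minimum is reached, "The site will have an option to continue recruitment until the maximum is reached" or the 8-week window closes. Section 12.3 says that "the final sample size will be based on site enrolment capabilities".

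**The concern.** Two limits for one primary hypothesis mean two pass marks. A safety result of 27/30 or 35/40 would succeed under 2.2.1 and fail under 12.1.2. Because study success needs both nulls rejected, that one count could decide the study. The conflict also undercuts the power statement in 12.3, which is said to be the same for both endpoints.

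The look at 20 raises a lesser question. It falls at the point where the site may choose to go on. Under 9.2, "The resulting interpretations regarding safety, effectiveness, and usability will be made by the physician overseeing" the case, and "All study outcome data captured will be compiled and analysed by the LABORIE study team". Under 12.4, "Randomization and/or blinding is not utilized in this study based on study design". No text says that the primary ratings are kept out of the look or out of the choice to continue.

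**Working it through.** **Inputs.** Null rate 75% (2.2.1, 12.1); true rate 96%, 1-sided 5%, N = 20, 30, 40 (12.3); limits 95% (2.2.1) and 97.5% (12.1.2).

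**Rule.** The lower 1-sided 100(1−α)% Clopper-Pearson limit for x of N exceeds 75% exactly when P(X ≥ x | N, 0.75) < α. The pass mark c is the smallest such x. Power is P(X ≥ c | N, 0.96).

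**Reproducing the plan at N=20.** P(X ≥ 19 | 0.75) = 20·0.75¹⁹·0.25 + 0.75²⁰ = 0.0211 + 0.0032 = 0.0243. This is below both 0.05 and 0.025. For 18 of 20 the 95% limit is only 71.7%, so c = 19 under either limit. Power = 20·0.96¹⁹·0.04 + 0.96²⁰ = 0.3683 + 0.4420 = 0.810, the plan's 81%.

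**Both limits, same formulas.**

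| N | c at 95% | P(X ≥ c) at 0.75 | Power | c at 97.5% | P(X ≥ c) at 0.75 | Power |
|---|---|---|---|---|---|---|
| 20 | 19 | 2.4% | 81.0% | 19 | 2.4% | 81.0% |
| 30 | 27 | 3.7% | 96.9% | 28 | 1.1% | 88.3% |
| 40 | 35 | 4.3% | 99.5% | 36 | 1.6% | 97.9% |

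The 95% columns agree with the stated 81%, 96% and 99% (the last two appear to be rounded down). The 97.5% columns do not agree at 30 or 40. The gap is wider at some sizes in between: power is 93.8% against 76.6% at N=23, and 91.6% against 72.1% at N=26.

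Direct limits show the split decision. For 27/30 the lower limit is 76.1% at the 95% level and 73.5% at the 97.5% level. For 35/40 it is 75.5% and 73.2%.

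**The look at 20, at a true rate of 75% and the 95% limit.**

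- *N chosen without the ratings:* P(X ≥ c | N, 0.75) is at most 4.9% for every N from 20 to 40 (the maximum is at 23).
- *Hypothetical rule, stop if cleared at 20, otherwise test once at a later N:* the error is P(X₂₀ ≥ 19) + P(X₂₀ ≤ 18 and X_N ≥ c_N). This gives 0.0243 + 0.0239 = 4.8% for N=30 and 0.0243 + 0.0326 = 5.7% for N=40. Over later N from 21 to 40 it runs from 2.4% to 6.0% (at 34). It exceeds 5% only at 23, 29, 34, 35 and 40, so 15 of the 20 later sizes stay at or below 5%.
- *Same hypothetical rule with the 97.5% limit for safety:* 2.8% at 30, 3.4% at 40, and at most 4.0%.

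**The case against.** **On the safety limit.** The 97.5% figure might be a deliberate, stricter criterion for safety, and the SAP is the later document and sets 5%. The stricter limit also cannot raise the false-success rate, and at N=20 it changes nothing. The last two points stand. The first does not fit 12.3, which declares identical power and no adjustment, or 2.2.1, which gives 95% for the same hypothesis. The SAP does not settle the matter, because it names no interval while protocol 12.5 points to the section with the odd figure.

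**On the look at 20.** A reader might infer that an open N, an unblinded rater and an interim at the minimum together inflate the type I error. The documents do not support that. Section 12.3 ties N to enrolment capability, 2.1 ends recruitment at 40 or at 8 weeks, and 12.7 gives the look a user-requirements purpose without statistical stopping criteria. No text describes stopping if the bound is cleared and continuing otherwise. Even under that rule, 20 then 30 stays below 5%, and because both nulls must be rejected the per-endpoint figure is an upper limit for false study success. What remains is that a stated purpose is not an exclusion. The SAP's assurance of no access to accumulating data covers only its author.

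**Conclusion.** The safety limit is wrong as written, and this does not depend on how the trial is run. Two sections give incompatible rules for a primary hypothesis. The consequence is one success in the pass mark at N=30 and N=40, none at N=20, and a loss of 8.6 points of safety power at N=30 (96.9% − 88.3%) and 1.6 points at N=40 (99.5% − 97.9%) if 12.1.2 is followed. These figures are exact binomial and rest on the plan's own 75% and 96%.

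The interim and the open N call only for an optional clarification. On the plan's stated basis for N, type I error per endpoint is at most 4.9%. The figures up to 6.0% (5.7% at N=40) apply only if the ratings drive the choice to continue, which is an assumption and not something the plan says.

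**What to change.** **Needed.** Change 97.5% to 95% in both places in 12.1.2, and name the 1-sided 95% Clopper-Pearson limit in the SAP for both hypotheses. This follows the sponsor's own error level and power statement. The cost is a handful of words, but the change eases the safety pass mark: at a true rate of 75%, the chance of passing rises from 1.1% to 3.7% at N=30 and from 1.6% to 4.3% at N=40, still within 5%. It should therefore be made before database lock, without sight of the safety tally, and with the reason recorded as the SAP's introduction requires.

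**Optional.** Add one sentence to 12.7 saying that neither the look at 20 nor the site's choice to continue uses the primary ratings. The site can keep its option to stop between 20 and 40, and suspension or termination under 7.7 is unaffected. The SAP is dated November 2018 and recruitment was proposed for July to September 2018. If that timetable held, the sentence can only record in the final report how N was in fact reached.
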